Internet-delivered Cognitive Behavior Therapy Compared to Stress Management for Atrial Fibrillation- a Randomized Controlled Trial With Active Control

Version 1. 2023-03-03. Established

Version 2. 2023-03-28. Changed title to match Clinical trials registration. Added logo.

This is analysis plan for the study approved by the Regional Ethics Committee in Stockholm on February 26, 2022 (reg no 2020-00197).

Clinical trials registration completed on June 24, 2021. Last update published on September 1, 2022.

ID: No: NCT04962932

Principal Investigator:

[name],

Department of Clinical Neuroscience, Division of Psychology

[name]

Karolinska Institutet, Stockholm, Sweden

Email: [contact],

[contact]

Statistical Analysis Plan

The primary outcome of the study is the difference between the treatment groups in AFEQT quality of life measured on a scale ranging from zero (severe symptoms and disability) to 100 (no symptoms and no disability). The patients are observed at baseline and again every week for twelve consecutive weeks. The difference between treatment groups in the mean quality of life score at twelve weeks is estimated with a linear mixed effect model. The quality-of-life score is the dependent variable.

The independent variables are a numeric time variable, a binary treatment indicator, and an interaction term between time and treatment. The model includes subject-specific random intercepts, which are assumed to follow a normal distribution. The random intercept can appropriately handle the potential temporal stochastic dependence in the data. The estimates for the parameter values are obtained by maximizing the corresponding likelihood function.

The linearity of the relationship between mean score and time assumed by the model is evaluated visually and tested formally by introducing restricted cubic splines for time in the model. Link functions are explored if necessary to ensure that the inferences on the mean are within the feasible bounded intervals of each outcome. The significance of each comparison is based on Wald's tests and deemed significant if below 5%.

Between group effect sizes are measured by the Cohen's d statistic, defined as the ratio between the mean score difference at twelve weeks and the baseline standard deviation of the score variable. Standard errors and confidence intervals are estimated with 5,000 cluster-bootstrap samples.

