All the secondary and exploratory outcomes are measured by numeric variables. They are analyzed with the same approach as the primary outcome. For the secondary outcomes (AFSS-visits, BSQ, SF-12, GSLTPAQ, ISI-5, PHQ-2, GAD-2, PCS) that have only two measurements over time (baseline and post-treatment) testing for departures from linearity is unfeasible.

The patterns and causes of possible missing values are investigated. The inflated statistical level resulting from the multiple comparisons is taken into account in the interpretation of the results and addressed in reports and manuscripts.

The main manuscript shows the results for the following secondary outcomes: SCL, CAQ, BSQ, SF-12, CSQ and AFFS-visits. The supplement shows the results for the following secondary outcomes: GSLTPAQ, PSS-4, PCS, ISI-5, PHQ-2 and GAD-2.

The measures of non-specific effects that are collected at week 2, Credibility Scale and Working Alliance Inventory are compared between the groups with the t-tests.

Adverse events are collected weekly and at post-treatment, at the latter timepoint with respect to the entire treatment period. The sum and mean severity rating of adverse events for each patient over the treatment period is compared between the groups with the t-test and the Mann-Whitney's U test, respectively. The incidence and severity rating of adverse events at post-treatment will be compared using t-test and Mann-Whitney U test, respectively.

Changes from post-treatment to six-month follow-up will be compared within each group only. No between-groups test will be performed on six-month data because the study was not powered to detect potential differences between the groups six months after treatment completion.

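### The six-month data are to be analysed only as within-group changes because the study was not powered for a comparison; an exploratory between-group estimate with an interval would be a cheap improvement

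*SAP*

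**What the plan says.** The last paragraph of the SAP sets the six-month analysis: "Changes from post-treatment to six-month follow-up will be compared within each group only". The reason follows at once: "No between-groups test will be performed on six-month data because the study was not powered to detect potential differences between the groups" at that time point. No other reason is given.

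Between-group effects on the outcome scales are defined at week 12 only. For the primary outcome, "The difference between treatment groups in the mean quality of life score at twelve weeks is estimated with a linear mixed effect model". Cohen's d is likewise "defined as the ratio between the mean score difference at twelve weeks and the baseline standard deviation of the score variable". Secondary outcomes follow the same approach.

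The paragraph on effect sizes already names an interval method: "Standard errors and confidence intervals are estimated with 5,000 cluster-bootstrap samples".

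What is ruled out in so many words is a between-group test. That no between-group estimate is planned either follows from the restriction to comparisons inside each arm, and from the absence of any six-month contrast elsewhere in the SAP.

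**The concern.** The title describes "a Randomized Controlled Trial With Active Control", yet the six-month data would be analysed without using that control. A change from post-treatment to six months in one arm combines any lasting or fading treatment effect with the natural course of symptoms. Two such changes, each judged on its own, do not estimate how the arms differ at six months or how far a week-12 difference has shrunk or grown.

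The stated reason does not carry the restriction. A study that is not powered for a comparison should make no confirmatory claim from it. It can still report the estimate and let the interval show how little or how much is known. Without this, a reader asking whether a week-12 benefit persists has no planned randomised estimate to consult, and any contrast produced later on request would be post hoc.

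**Working it through.** **No figure to reproduce.** The SAP states no sample size, power, standard deviation, target effect, allocation ratio or retention. Everything numerical below is illustration under assumed inputs.

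**1. Relative precision for a weekly outcome.** From the SAP: baseline plus twelve weekly scores (13 visits), linear time, random intercept. Assumed: single-visit variance 1, within-patient correlation ρ of 0.5 or 0.7, complete weekly data, six-month retention q of 80% or 70% with data missing at random (dropout taken as unrelated to the scores, the simplest case), and a separate six-month mean in each arm. The correlation c of six-month with weekly scores is either ρ or ρ − 0.2. Variances are per arm and per patient, and week 12 is taken as post-treatment.

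- Week 12: V12 = ρ + (1 − ρ)(1/13 + 36/182) = ρ + (1 − ρ) × 0.2747. This gives 0.5 + 0.5 × 0.2747 = 0.637 and 0.7 + 0.3 × 0.2747 = 0.782.
- Share of six-month variance explained by the weekly mean: R² = c² / (ρ + (1 − ρ)/13).
- Six months: V6 = (1 − R²)/q + R².
- Change from week 12 to six months: Vc = V6 + V12 − 2c.
- Ratio of standard errors to week 12: √(V6/V12) and √(Vc/V12). With the same inputs in both arms, the ratios also hold for between-group differences.

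Example, ρ = c = 0.5 and q = 80%: R² = 0.25/0.5385 = 0.464; V6 = 0.536/0.8 + 0.464 = 1.134; Vc = 1.134 + 0.637 − 1 = 0.771; ratios √(1.134/0.637) = 1.33 and √(0.771/0.637) = 1.10.

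| ρ | c | q | R² | V6 | ratio, six-month difference | Vc | ratio, change in difference |
|---|---|---|---|---|---|---|---|
| 0.5 | 0.5 | 80% | 0.464 | 1.134 | 1.33 | 0.771 | 1.10 |
| 0.5 | 0.5 | 70% | 0.464 | 1.230 | 1.39 | 0.867 | 1.17 |
| 0.7 | 0.7 | 80% | 0.678 | 1.081 | 1.18 | 0.463 | 0.77 |
| 0.7 | 0.7 | 70% | 0.678 | 1.138 | 1.21 | 0.521 | 0.82 |
| 0.5 | 0.3 | 80% | 0.167 | 1.208 | 1.38 | 1.246 | 1.40 |
| 0.5 | 0.3 | 70% | 0.167 | 1.357 | 1.46 | 1.394 | 1.48 |
| 0.7 | 0.5 | 80% | 0.346 | 1.164 | 1.22 | 0.946 | 1.10 |
| 0.7 | 0.5 | 70% | 0.346 | 1.280 | 1.28 | 1.063 | 1.17 |

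The 0.77 needs the correlation to stay at 0.7 all the way to six months; lowering it by 0.2 turns that case into 1.10.

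**2. Absolute precision.** This depends on a sample size that the SAP does not give. For an unadjusted standardised difference with n patients per arm contributing, the 95% half-width is 1.96 × √(2/n): 0.51 SD at an assumed n of 30, and 0.28 SD at an assumed n of 100.

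**3. Why two within-arm results are a poor substitute.** Suppose both arms share the same true change, and each within-arm test is significant with probability p. Exactly one arm is then significant with probability 2p(1 − p): 2 × 0.05 × 0.95 = 9.5% when there is no change, 32% at p = 0.2 or 0.8, and 50% at p = 0.5. This matters only if someone sets the two results side by side.

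**The case against.** The strongest reply is that this is a legitimate, disclosed restriction. The SAP fixes week 12 as the only between-group time point, declines a later comparison that it was not powered for, says so, and makes no claim about durability. That stands. A reader might infer that the SAP contradicts itself, or that it will judge durability by whether one arm's change is significant and the other's is not. The text supports neither reading. It nowhere proposes to set one arm's result against the other's, and its no-test sentence is already a partial caution.

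Second, the arms are independent, so if each arm's change were reported with its standard error, the difference in change would follow by subtraction, with standard error √(SE₁² + SE₂²). This is right, but it covers only half of the need, and the SAP does not commit to that reporting. The standard error of the six-month difference itself would also need its covariance with the week-12 estimate.

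Third, selective follow-up threatens a between-group contrast as well as a within-group change, and a likelihood model gives both the same protection. This stands, so dropout is no argument for one over the other.

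Fourth, the SAP does not say whether either arm may receive the other treatment after week 12. If so, the contrast still compares the groups as randomised, but means something different. This stands as a condition on interpretation.

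Fifth, a ratio to an unknown week-12 standard error cannot show that the interval would be useful. This also stands.

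**Conclusion.** The point holds as a modest improvement that should be made. Lack of power supports an exploratory label; it does not support omitting the randomised contrast in favour of two uncontrolled changes. The SAP contains no error or contradiction here, and the week-12 primary analysis is untouched.

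Its size cannot be stated for this trial. Standard-error ratios of about 1.18 to 1.46 for the six-month difference and 0.77 to 1.48 for the change in difference rest wholly on assumed correlation, retention and missing-at-random dropout. A reader might conclude from them that the interval would be wider but still informative, or that six-month power is known to be low. Neither follows: the week-12 standard error is unknown, and the SAP says only that the study was not powered, without a figure.

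**What to change.** For each outcome that has six-month data, add the between-group difference at six months and the between-group difference in change from post-treatment to six months. Give both with 95% confidence intervals, labelled exploratory and without a significance claim.

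- Weekly outcomes: fit a separate mixed model that adds a categorical six-month term and its interaction with treatment. Leave the twelve-week model as it is.
- Any outcome measured only at baseline, post-treatment and six months: use a mixed model with categorical time.
- Keep the within-group changes as descriptive estimates with intervals, and state that they support no conclusion about differences between groups or relative durability.
- State that the contrast compares groups as randomised, that any access to the other treatment after week 12 must be considered in its interpretation, and that it relies on six-month data being missing at random.

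The cost is a few sentences and one further model per outcome, on data that the SAP already intends to analyse and with the cluster bootstrap that it already names. The downsides are that intervals may be wide and include zero, and that there are more exploratory contrasts to report alongside the multiplicity that the SAP already acknowledges.
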